2. SCHEDULE OF EVALUATIONS

Study procedures	Pre-screening	Screening ¹ (from day -7 to day 0)	Baseline (T0)	T7	T14 (End of treatment)	T21	T28	ETDV ⁵	3 Months
				Week 1	Week 2	Week 3	Week 4		
Laboratory-confirmed SARS-CoV-2 infection	X*								
Electronic Informed Consent signature		X							
Demographic data and life style recording		X							
Medical/surgical History and underlying disease		X							
Vital signs daily measurement (BP, PR, BT) and transdermal oxygen saturation (SpO2)									
Pregnancy Test ² (female only)				X	X	X			
Laboratory analyses ³				X	X	X	X		
NEWS score evaluation				X	X	X		X	
Inclusion/Exclusion Criteria			X						
Randomization		X							
IMP daily administration						X**			
Nasopharyngeal swabs					X	X		X	
Supplemental oxygen therapy (NEWS ≥ 2) and/or					X	X		X	

Study procedures	Pre-screening	Screening ¹ (from day -7 to day 0)	Baseline (T0)	T7	T14 (End of treatment)	T21	T28	ETDV ⁵	3 Months
				Week 1	Week 2	Week 3	Week 4		
mechanical ventilation (Yes/No)									
ICU admission (Yes/No)				X	X		X		
Study drug dispensation			X						
Verify study medication dosing compliance				X	X				
AEs / SAEs / CMs Record and assessment ⁴					X			X	
QoL questionnaire (EQ5D5L)									X

* Confirmation of SARS-CoV-2 infection must be available before the screening visit. Only diagnosed COVID-19 paucisymptomatic patients will be evaluated for the trial participation

** After an administration of two oral doses in the first day of treatment (one dose in the morning and one dose in the evening, each dose administered with 2 capsules containing 60 mg of the active substance or placebo), patients will take on a single daily oral dose, for a total of 14 days of treatment

1. Screening visit will be carried out within 7 days from the diagnosis of SARS-CoV-2 infection
2. Urine pregnancy test will be done at patient's domicile
3. Laboratory Analyses:

Biochemistry (T0, T7, T14, T21, T28)

Sodium
Potassium
Chloride
Urea
Uric acid
Creatinine
Calcium
Inorganic phosphorus
Fasting Glucose
Total and direct bilirubin
Total protein
Albumin
Alpha-1 Globulins

Haematology (T0, T7, T14, T21, T28)

Haemoglobin
Red cell count
Packed cell volume
Mean cell volume
Mean cell haemoglobin
Mean cell haemoglobin concentration
Platelet count
White cell count
Neutrophils
Lymphocytes
Monocytes
Eosinophils
Basophils

Alpha-2 Globulins	
Beta Globulins	
Alkaline phosphatase	Coagulation (T0, T7, T14, T21, T28)
AST	Prothrombin time
ALT	Activated partial thromboplastin time

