4. SELECTION OF STUDY POPULATION

For the purpose of the study the following definition are applied.

A case of COVID-19 is a person with SARS-CoV-2 infection as determined by an approved molecular test (PCR) from an adequate sampling of upper respiratory tract irrespective of clinical signs and symptoms.

A paucisymptomatic case of COVID-19 who does not need immediate admission to hospital and has a national early warning score (NEWS) ≤ 2 .

NEWS score has been revised on 2019 by England and Wales National Health Service as following²⁴:

Element	Score						
	3	2	1	0	1	2	3
Respiratory rate	≤ 8		9-11	12-20		21-24	≥ 25
SpO ₂	≤ 91	92-93	94-95	≥ 96			
Oxygen		Yes		NO			
Systolic Blood Pressure	≤ 90	91-100	101-110	111-219			≥ 220
Pulse	≤ 40		41-50	51-90	91-110	111-130	≥ 131
ACVPU				A			C,V,P,U
Temperature, °C	≤ 35.0		35.1-36.0	36.1-38.0	38.1-39.0	≥ 39.1	

ACVPU: Alert, Confusion, Voice, Pain, Unresponsive

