7. ENDPOINTS

7.1. STUDY ENDPOINTS

7.1.1. Primary endpoints

Virologic outcome. Proportion of participants with undetectable SARS-CoV-2 at PCR at day 7 after randomization.

Clinical outcome. Proportion of participants who not requires supplemental oxygen therapy (NEWS ≤ 2) and/or mechanical ventilation at day 14 after randomization.

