9.5.2.2. Secondary analyses

All secondary endpoints will be analyzed at each available timepoints by means of descriptive statistics and by appropriate parametric tests depending on the nature of the variable and its distribution. Data transformation might be used in order to satisfy the assumption of normality requested by parametric statistical tests. In case such assumptions are not met, non-parametric counterpart tests will be used. Change from baseline value (for continuous variables) and shift tables versus baseline (for categorical variables) will also be summarized for all post-baseline visits.

The incidence of participants with undetectable SARS-CoV-2 at PCR, the incidence of participants who requires supplemental oxygen therapy (NEWS ≤ 2) and/or mechanical ventilation, and mortality will be analyzed as proportion at each time point and as time-to-event.

Details will be provided in the SAP.

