14.1.1 PRIMARY EFFICACY ENDPOINTS AND ANALYSES

1. Proportion of patients with undetectable SARS-CoV-2 at PCR at day 7 after randomization (virologic endpoint). This endpoint will be derived as below.
 - Based on Approved molecular test (PCR) result at day 7, the responses will be considered as “detectable” if PCR result is “Positive” otherwise “undetectable” if PCR result is “Negative” (Missing PCR result will be considered as missing in the main analysis).

The response (detectable / undetectable) at day 7 will be analysed using Binary logistic regression model with treatment group and pre-defined baseline factors (center, age, status and their interaction effects with treatment group). Odds ratio

will be computed for comparisons of each active treatment group versus placebo. i.e., raloxifene (60 mg) versus placebo and raloxifene (120 mg) versus placebo.

2. The proportion of patients who does not require supplemental oxygen therapy (NEWS ≤ 2) and mechanical ventilation at day 14 after randomization (clinical endpoint). This endpoint will be derived as below.

- If collected NEWS score > 2 or mechanical ventilation at day 14 result “Yes” then the response will be considered as “Required”. If collected NEWS score ≤ 2 and mechanical ventilation with result “No” then the response will be considered as “Not Required” (if both NEWS score and mechanical ventilation are missing, patient will be considered as missing).

The response (Required/ Not required) at day 14 will be analysed using Binary logistic regression model with treatment group and pre-defined baseline factors (center, age, status, baseline NEWS and their interaction effects with treatment group). Odds ratio will be computed for comparisons of each active treatment group versus placebo. i.e., raloxifene (60 mg) versus placebo; and raloxifene (120 mg) versus placebo.

For both virologic and clinical endpoint, Binary Logistic regression will be performed using PROC GENMOD in SAS® on the observed data only to estimate difference in proportions between each active treatment versus placebo and its corresponding 95% (2-sided) confidence intervals. Exponential transformation will be used to obtain the odds ratio and corresponding 95% confidence interval. P-values will be reported based on the Wald tests from Type III analyses. Bonferroni method will be considered to handle multiple treatment comparisons.

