14.1.2 SECONDARY EFFICACY ENDPOINTS AND ANALYSES

1. Proportion of patients with undetectable SARS-CoV-2 at PCR at day 14 after randomization at day 28 after randomization. Analyses will be performed on FAS population. This endpoint will be derived as below

- Based on Approved molecular test (PCR) result, the responses will be considered as “detectable” if PCR result is “Positive” otherwise “undetectable” if PCR result is “Negative” (Missing PCR result will be considered as missing).

The response (detectable / undetectable) at day 14 and day 28 will be analysed using repeated measures logistic regression model with treatment group, visit and pre-defined baseline factors (center, age and status). Odds ratio will be computed for comparisons of each active treatment group versus placebo at each assessment day i.e., raloxifene (60 mg) versus placebo; and raloxifene (120 mg) versus placebo. Analyses will be performed on FAS population using observed data only.

2. Proportion of patients who does not require supplemental oxygen therapy (NEWS ≤ 2) and mechanical ventilation at day 7 and 28 after randomization. This endpoint will be derived as below

- If collected NEWS score > 2 or mechanical ventilation with result “Yes” then the response will be considered as “Required”. If collected NEWS score ≤ 2 and mechanical ventilation with result “No” then the response will be considered as “Not Required” (if both NEWS score and mechanical ventilation are missing, patient will be considered as missing).

The response (Required / Not Required) at day 7 and day 28 will be analysed using repeated measures logistic regression model with treatment group, visit and pre-defined baseline factors (center, age, status and baseline NEWS). Odds ratio will be computed for comparisons of each active treatment group versus placebo at each assessment day. i.e., raloxifene (60 mg) versus placebo; and raloxifene (120 mg) versus placebo. Analyses will be performed on FAS population using observed data only.

For the above two secondary endpoints, Repeated Measures Logistic regression will be performed using PROC GENMOD in SAS® on the observed data only to estimate difference in proportions between each active treatment versus placebo and its corresponding 95% (2-sided) confidence intervals. Exponential transformation will be used to obtain the odds ratio and corresponding 95% confidence interval. P-values will be reported based on the Wald tests from Type III analyses.

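### The clinical primary endpoint as derived in SAP 14.1.1 is 'NEWS ≤ 2 and not ventilated'; it can pass a patient on oxygen, leaves two missing-data patterns unscored and may lose withdrawn failures

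*SAP*

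**What the plan says.** Protocol 7.1.1 defines the clinical primary endpoint as "Proportion of participants who not requires supplemental oxygen therapy (NEWS ≤ 2) and/or mechanical ventilation at day 14 after randomization". SAP 3.2.1 repeats the NEWS gloss. The objective in SAP 3.1.1 does not mention NEWS: it names need for oxygen or ventilation within 14 days of starting therapy.

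SAP 14.1.1 item 2 turns this into a rule. A patient is *Required* (failure) under "If collected NEWS score > 2 or mechanical ventilation at day 14 result" Yes, and *Not Required* (success) if NEWS is at most 2 and ventilation is No. The only missing-data clause is "if both NEWS score and mechanical ventilation are missing, patient will be considered as missing". SAP 14.1.2 item 2 reuses the rule at days 7 and 28 ("If collected NEWS score > 2 or mechanical ventilation with result"). SAP Table 3 says that missing data are not imputed.

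The NEWS label varies within the protocol. The schedule in Section 2 has a row reading "Supplemental oxygen therapy (NEWS ≥ 2) and/or" and, continuing, "mechanical ventilation (Yes/No"). Section 9.5.2.2 speaks of "the incidence of participants who requires supplemental oxygen therapy (NEWS ≤ 2) and/or mechanical ventilation", which attaches the low score to patients who do need oxygen. In Section 4 the paucisymptomatic case definition includes that the patient "has a national early warning score (NEWS) ≤ 2".

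On follow-up, Protocol 6.2.4 withdraws patients from the study once they meet criteria for oxygen or ventilation. Protocol 6.3 keeps patients who stop treatment under observation, but also lists disease progression as a reason to leave the study. SAP 7.3.2 lists progression as a reason for stopping treatment only.

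**The concern.** NEWS is a total over seven items, of which oxygen is one and contributes 2 points. A cut-off on the total therefore need not agree with whether a patient is on oxygen. It can err in both directions, and the direction that calls a patient on oxygen a success contradicts the endpoint's own words.

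The second worry is loss of failures. The rule is applied to observed data at the day 14 visit. If a patient is withdrawn on day 6 because oxygen criteria are met, there may be no day 14 NEWS or ventilation entry, and the patient leaves the analysis instead of counting as a failure. If that happens more often in one arm, the comparison is biased.

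The stake is that, under SAP 14.1.1, rejecting any one null hypothesis establishes superiority. This endpoint can therefore carry the claim alone.

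**Working it through.** **Inputs.** NEWS bands from SAP Appendix 3; the scoring rule from SAP 14.1.1 item 2; 68 patients from SAP 4.3. The plan gives no figure of its own on this point to reproduce.

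**1. Band combinations.** Respiratory rate 5 bands, SpO2 4, systolic BP 5, pulse 6, ACVPU 2, temperature 5: 5 × 4 × 5 × 6 × 2 × 5 = 6,000 combinations for each oxygen state. These count possible profiles, not patients.

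- On oxygen (2 points), a total of at most 2 requires every other item at 0. That is 1 combination, total exactly 2; with ventilation No it is *Not Required*.
- Room air (0 points): 1 combination totals 0, 7 total 1 and 24 total 2, so 1 + 7 + 24 = 32 are at or below the cut-off.
- Room air, total exactly 3: 62 combinations. By SpO2 band: ≥ 96, 38; 94-95, 17; 92-93, 6; ≤ 91, 1 (38 + 17 + 6 + 1 = 62).

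**2. A room-air failure with normal saturation.** SpO2 97 (0) + temperature 38.5 (1) + pulse 95 (1) + systolic BP 105 (1) = 3, with respiratory rate and consciousness normal: *Required*. Fever alone scores at most 2 and does not cross the cut-off.

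**3. Overlap with the protocol's own alarm values.** With SpO2 at 0, eight single bands reach 3 alone. Against the triggers in Protocol 6.2.2 for patients it calls critical:

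- four lie wholly inside: systolic BP ≤ 90, systolic BP ≥ 220, pulse ≥ 131, altered ACVPU;
- two differ only at the boundary value: pulse ≤ 40 and temperature ≤ 35.0;
- two have no matching trigger: respiratory rate ≤ 8 and ≥ 25.

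The profile in step 2 meets none of the numerical triggers.

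**4. Scoring grid.**

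| NEWS | Ventilation Yes | Ventilation No | Ventilation missing |
|---|---|---|---|
| > 2 | Required | Required | Required |
| ≤ 2 | Required | Not Required | **no rule** |
| missing | Required | **no rule** | Missing |

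Five cells are *Required*, one *Not Required*, one missing and two unscored (5 + 1 + 1 + 2 = 9). A non-ventilated patient on oxygen without a day 14 NEWS falls in the second unscored cell. The no-imputation entry in Table 3 does not settle these cells, because the SAP calls a patient missing only when both components are missing.

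**5. Labels.** A NEWS of exactly 2 meets both the schedule's ≥ 2 label and the endpoint's ≤ 2 label: 24 room-air + 1 on-oxygen = 25 combinations. The SAP's scoring is not affected, since its cut-off of > 2 is explicit.

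**6. Route to a lost failure.** Protocol 6.2.4 withdraws the patient. The discontinuation visit in Protocol 6.3 covers physical abnormalities, vital signs and saturation, but not oxygen use. SAP 7.3.1 uses nominal-visit data for by-visit summaries. SAP 14.1.1 analyses observed data only. If all four apply, the outcome is missing.

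**7. Weight of one patient.** Assuming an even split of 68 with all patients observed, arms of 22 to 24: 100/24 = 4.2, 100/23 = 4.3, 100/22 = 4.5 percentage points.

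**The case against.** NEWS ≤ 2 is written into the protocol endpoint (synopsis, 7.1.1, 9.5.2.1) and matches the case definition, so staying at or below 2 has a clear clinical meaning. An endpoint of not needing oxygen requires some operational criterion; the protocol chose one and the SAP applies it. Many room-air profiles that score as failures are ones the protocol itself treats as alarming. NEWS, hospital admission, intensive care and survival are reported separately in SAP 14.1.2. The phrase about observed data suggests that the two open cells would be excluded by default. SAP 7.3.2, by not listing progression as a reason to leave the study, suggests that such patients may stay.

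Most of this stands. It rules out calling the SAP rule a departure from the protocol, and it makes scoring sick room-air patients as failures defensible. It does not defend counting a patient on oxygen as a success, it leaves a programmer to choose a rule for two cells of a primary endpoint, and it does not remove the contradiction on who leaves the study.

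A reader might also infer that the planning rates (50% and 75%, SAP 4.1.2) prove that pure oxygen need was meant. They do not: Protocol 2.1 puts severe plus critical disease at 14% + 6% = 20%, so a 50% placebo failure rate may sit closer to a broader clinical status.

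**Conclusion.** The clinical primary endpoint, as derived, is NEWS ≤ 2 without ventilation, and should be read and labelled as such. Three gaps need closing before unblinding: one on-oxygen profile that counts as a success, two patterns without a rule, and possible loss of failures if Protocol 6.2.4 is followed. The first is narrow (one combination). The second and third depend on how many records are incomplete, which the documents do not show.

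A reader might infer that the NEWS rule should be replaced as the tested definition, or that a loss of power can be put on the misclassification. The documents support neither. The rule is prespecified and enrolment has already stopped. Any dilution or power figure would rest on invented error rates, so none is claimed. Nor do the documents show that failures will be lost; they show only that the text allows it. The 4.2 to 4.5 point figure is the weight of a single patient under an assumed even split, not an estimate of error.

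**What to change.** Before unblinding, and recorded in SAP Section 18:

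- **Tested definition.** Keep the protocol-worded NEWS ≤ 2 rule for the hypothesis test, add a recorded Yes on the NEWS oxygen item to *Required*, and label the results as NEWS-based clinical status.
- **Sensitivity analysis.** Score *Required* from recorded oxygen use or ventilation. Use the Yes/No row of the protocol schedule only if a check blind to treatment shows that sites did not complete it as a NEWS cut-off. This assumes that the fields exist in the eCRF, which is not among the documents.
- **Withdrawn patients.** Score a patient withdrawn for meeting oxygen or ventilation criteria before day 14, with no day 14 record, as *Required*. State openly that this carries an earlier status forward to an endpoint defined at day 14.
- **Open patterns.** Treat NEWS ≤ 2 with ventilation missing, and NEWS missing with ventilation No, as missing unless oxygen use is recorded, in which case *Required*.
- **Consistency.** Apply the same rules at days 7 and 28. Align the NEWS labels in Protocol Sections 2, 7.1.1 and 9.5.2.2. Reconcile Protocol 6.2.4 and 6.3 with SAP 7.3.2 on whether patients meeting oxygen criteria leave the study.

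The cost is a small documented departure from the protocol wording, a few lines of derivation and one extra analysis. If the eCRF holds the oxygen fields, no new data are needed.

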9. STATISTICS

9.1. SAMPLE SIZE

The sample size of the study is calculated based on the following assumptions:

- Virologic assumption: Early treatment with antivirals increases the proportion of patients with undetectable SARS-CoV-2 in upper respiratory tract at day 7 after therapy from 25% to 50%;
- Clinical assumption: Early treatment with antivirals increases the proportion of participants who recover without need of mechanical ventilation and/or supplemental oxygen therapy by the day 14 after therapy from 50% to 75%.

Based on these assumptions and considering a randomization ratio 1:1:1, the sample size will be adaptively determined to achieve a power greater than 80% to show superiority of raloxifene vs placebo in terms of either one primary endpoint (section 7.1.1) and controlling the one-sided alpha below 0.025.

Sample size will be determined through the following steps:

- an interim analysis will take place when 50 participants per arm (N=150) have reached their primary endpoints (i.e. assessments available).
 - In case of efficacy of at least one treatment arm or futility of both arms (see criteria in section 9.3) the study enrolment will be stopped,
 - otherwise the actual number of new participants in each arm may be blindly reassessed according to observed efficacy of the best favourable and promising arm;
- in case of continuation of the study to the final stage, it is expected to randomize on average additional 174 patients, depending on sample size reassessment and possible dropping of an ineffective treatment arm. Expected sample size will be between 250 and 450 randomized participants;
- drop-outs of randomized subjects will not be replaced.

This approach allows either to minimize the number of enrolled participants if the experimental assumptions are too conservative or to have a good power level if they are too optimistic.

Pocock's spending functions and conditional power (CP) will be used to control the type I and II errors, considering that interim analysis will be performed when half of the initial planned patients have been reached the primary endpoints (i.e. assessments available).

Bonferroni method is used to adjust for multiple endpoint vs treatment comparisons.

Sample size calculation has been performed through simulation (100000 replications). The statistical software used for simulation was SAS®, Version 9.4.

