3.1.1 PRIMARY OBJECTIVES

- Evaluation of the effectiveness of therapy in reducing the proportion of patients who still have viruses in the upper airways after 7 days of therapy.
- Evaluation of the effectiveness of therapy in reducing the proportion of patients who requires supplemental oxygen therapy and/or mechanical ventilation within 14 days of starting therapy.

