In the SAS® procedure PROC GENMOD, a Type III analysis will be performed by adding the model options: TYPE3, DIST=BIN and LINK=LOGIT. REPEATED statement will be used to consider visit and TYPE=UN option used for correlation-matrix. If the model does not converge then appropriate TYPE would be applied for correlation-matrix.

The following time-to-event endpoints will be analysed according to SAP section 4.4 methods.

- i. Time to reach undetectable SARS-CoV-2 at PCR
- ii. Time to get relieved from supplemental oxygen therapy (NEWS ≤ 2) and/or mechanical ventilation
- iii. Overall survival

Analyses will be performed on FAS population.

3. Proportion of patients in each NEWS category at Day 7, 14 and 28 after randomization will be summarized by frequency and percent by treatment and visit for FAS population.
4. NEWS score at Day 7, 14 and 28 after randomization will also be summarized using descriptive statistics by treatment and visit for FAS population.
5. Proportion of hospitalized patients who at the beginning of the study were at domicile isolation at day 7, 14 and 28 after randomization will be analysed using comparison of proportions (i.e comparisons of each active treatment group versus placebo at each assessment day) through Fisher's exact test and will be summarized using frequency and percent by treatment and visit. Analyses will be performed on FAS population.

6. Proportion of patients admitted to intensive care at Day 7, 14 and 28 after randomization will be analysed using comparison of proportions (i.e comparisons of each active treatment group versus placebo at each assessment day) through Z-test and will be summarized using frequency and percent by treatment and visit. Analyses will be performed on FAS population.
7. Overall survival will be analysed according to time-to-event methods described in SAP section 4.4.
8. Quality of life questionnaire (EQ-5D-5L) at 3 months after the randomization will be summarized using appropriate descriptive statistics by treatment. The number and proportion of subjects of each level (1 - no problems, 2 - slight problems, 3 - moderate problems, 4 - severe problems, 5 - extreme problems) for each dimension (mobility, self-care, usual activities, pain/discomfort, and anxiety/depression) will be reported.
Analyses will be performed on FAS population.

Patient's data will be listed for all secondary endpoints.

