15.1.2 ADVERSE EVENT ANALYSIS

All AEs will be coded by System Organ Class (SOC) and Preferred Term (PT) according to The Medical Dictionary for Regulatory Activities (MedDRA) September 2020, version 23.1.

Pre-treatment AEs will be presented in the listings only.

- Proportion of patients with any adverse event (grade \leq 2 according to CTCAE) within Day 7, 14 and 28 after randomization will be analysed using comparison of proportions (i.e comparisons of each active treatment group versus placebo at each assessment day) through Fisher's exact test and will be summarized using frequency and percent by treatment and visit. Analyses will be performed on FAS population.
- Proportion of patients with severe adverse events (grade \geq 3 according to CTCAE) within Day 7, 14 and 28 after randomization will be analysed using comparison of proportions (i.e comparisons of each active treatment group versus placebo at each assessment day) through Fisher's exact test and will be summarized using frequency and percent by treatment and visit. Analyses will be performed on FAS population.

TEAE summaries will be presented, displaying frequencies and Percentages of patients reporting AEs within each SOC in decreasing order of total frequency according to the number of patients reporting the SOC and the AE within the SOC by treatment. Along with AEs, incidence will be reported. On each of these

summaries, patients will be counted only once per SOC, even if they experience multiple AEs within the same SOC. Patients will be counted only once per preferred term, even if they experienced the same adverse event more than once.

For the summary by severity (Mild, Moderate, Severe, Life-threatening or disabling, Death), patients will be classified by the most severe level of the adverse event experienced when they experienced the same adverse event (or AE within SOC) more than once.

The severity of AEs and SAEs will be graded using the CTCAE version 5.0. Any AE not listed in the CTCAE will be graded as follows:

1. Mild
2. Moderate
3. Severe
4. Life-threatening or disabling
5. Death

For summaries, the drug-event relationship will be assessed as “None”, “Unlikely”, “Possible” “Probable” or “Highly probable”. Any AE reported in the study having a possible, probable or highly probable relationship to study drug will be defined as “Adverse Drug Reaction” (ADR).

The following events will be considered adverse events of special interest:

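### The primary clinical objective covers oxygen or ventilation need at any time up to day 14, but the SAP scores status on day 14 only, so earlier need is never counted as a failure.

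*SAP*

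**What the plan says.** **Objective (cumulative).** SAP 3.1.1 aims to reduce the proportion of patients who "requires supplemental oxygen therapy and/or mechanical ventilation within 14 days of starting therapy". The protocol synopsis has the same objective, and protocol 3.1 uses *by* day 14.

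**Sizing (cumulative).** Protocol 9.1 assumes that treatment raises the proportion who "recover without need of mechanical ventilation and/or supplemental oxygen therapy by the day 14 after therapy from 50% to 75" per cent. SAP 4.1.2 repeats this.

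**Endpoint (one day).** Protocol 7.1.1 and SAP 3.2.1 define the clinical outcome *at* day 14. SAP 14.1.1 derives *Required* with a rule that begins "If collected NEWS score > 2 or mechanical ventilation at day 14 result". NEWS of 2 or less with no ventilation is *Not Required*. Table 3 and 14.1.1 restrict the analysis to observed data without imputation.

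**Patients who meet the oxygen criteria.** Protocol 6.2.4 withdraws them from the study. Protocol 6.3 keeps patients who stop study drug under efficacy follow-up, yet lists documented disease progression as a reason for leaving the study. SAP 7.3.2 lists progression under treatment discontinuation but not under study discontinuation.

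**Time to event.** Protocol 9.5.2.2 plans a time-to-event analysis of the incidence of requiring oxygen or ventilation. SAP 14.1.2 and 14.1.3 define it as time to being relieved of them.

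**The concern.** The trial's stated aim is to prevent progression. Oxygen need that begins and ends before day 14 is progression, and the primary clinical endpoint has no way of scoring it as such. A day-14 reading mixes two things: whether a patient got worse, and whether a patient who got worse had recovered by the visit. The reported result could then differ in either direction from the answer to the stated objective. The 50% and 75% planning rates also describe a different variable from the one that will be analysed.

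**Working it through.** **1. Follow one patient through the rules.** Take a patient on oxygen from day 4 to day 11 with NEWS 1 and no ventilation on day 14.
- Followed under protocol 6.3: the day-14 record is complete and the score is *Not Required*, a success.
- Withdrawn under protocol 6.2.4: there is no day-14 NEWS or ventilation entry, so the patient is missing and drops out of the model.

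On neither path is the earlier need scored as a failure.

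**2. Look for another analysis that recovers it.** Patients enter with no need of oxygen (inclusion criterion 7), and paucisymptomatic is defined as NEWS of 2 or less (protocol 4). Time to relief is therefore not time to first need. The day-7 item in SAP 14.1.2 is another single-day reading. SAP 7.3.1 keeps unscheduled measurements out of the by-visit summaries. First need is not the event in any inferential analysis, and SAP section 18 does not list the change of time-to-event definition.

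**3. Reproduce the plan's figures.** Protocol 9.1 promises that "the sample size will be adaptively determined to achieve a power greater than 80" per cent while "controlling the one-sided alpha below 0.025".
- Two endpoints × two doses = 4 tests, so 0.025/4 = 0.00625 one-sided each.
- Two looks with a constant boundary c at half the information: P(Z1 > c or Z2 > c) = 0.00625, with correlation √0.5, gives c = 2.6964. This matches protocol Table 1.
- The interim is at 50 per arm, half the initial plan, so n = 100 per arm.
- Fixed-design power = Φ[(d − z·se0)/se1], with d = 0.25, z = 2.4977, se0 = √(0.625 × 0.375 × 2/100) = 0.0685 and se1 = √((0.25 + 0.1875)/100) = 0.0661. This is Φ(1.19) = 88.4%.
- A two-look simulation at Z > 2.6964, without futility or size reassessment, gives 85.2%.

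The stated power above 80% is supported if the rates are 50% and 75%.

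**4. Effect of the day-14 reading.** Let r be the share of patients who needed support but had recovered by day 14, equal in both arms. It is an assumption; the documents give no value.

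Counted as successes, the success rate is p + r(1 − p):

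| r | Placebo | Active | Power, 100 per arm | n per arm for 80% |
|---|---|---|---|---|
| 0 | 50% | 75% | 88% | 83 |
| 0.1 | 55% | 77.5% | 81% | 98 |
| 0.3 | 65% | 82.5% | 63% | 140 |
| 0.5 | 75% | 87.5% | 41% | 217 |

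Left out as missing, the success rate is p/(1 − r(1 − p)):

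| r | Placebo | Active | Power, 100 per arm randomized |
|---|---|---|---|
| 0.1 | 52.6% | 76.9% | 86% |
| 0.3 | 58.8% | 81.1% | 78% |
| 0.5 | 66.7% | 85.7% | 65% |

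If every patient with need were withdrawn and missing, both arms would read 100%.

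**5. Validity when r differs by arm (illustrative).**
- No preventive effect, 50% need in both arms, recovered shares 30% on placebo and 50% on active: 1 − 0.5 × 0.7 = 65% versus 1 − 0.5 × 0.5 = 75%. A 10-point difference appears with no prevention.
- True 50% versus 75% free of need, half of the placebo cases recovered and none of the active: 1 − 0.5 × 0.5 = 75% versus 75%. A real 25-point effect disappears.

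**6. At the actual size.** SAP 4.3 reports 68 patients, about 23 per arm. Clinical power at 50% versus 75% is 22% at one-sided 0.00625 and 16% at Z > 2.6964, before any dilution.

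**The case against.** The SAP implements the endpoint that the protocol defines, so the mismatch is inherited. Replacing a primary endpoint after enrolment has stopped is a serious step, and adding a cumulative analysis might be enough. This has weight. But the same protocol states the objective and sizes the trial cumulatively, and a change that is declared before unblinding and keeps the day-14 reading alongside answers most of it.

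The example patient would also be *Required* on day 7 if assessed then, and would show in the by-visit tables. That is true, but it depends on the episode covering the visit and leaves the primary result unchanged.

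Three stronger readings are tempting, and the documents do not support them:
- *Every patient with early need is counted as a success.* Protocol 6.2.4 withdraws such patients, and those without a day-14 record would be missing instead. Which path applies is unclear, because 6.2.4 and 6.3 conflict.
- *The snapshot misses most events and power collapses.* This needs an onset pattern and an oxygen duration that the documents do not give. With uniform onset over 14 days and exponential duration of mean d, the share still on oxygen at day 14 is (d/14)(1 − exp(−14/d)): 39% for d = 6 but 54% for d = 10. In the second case most cases are still visible. The SAP variable is also NEWS above 2 or ventilation, not oxygen use as such.
- *Hospitalisation and ICU have the same contradiction.* No objective asks for them within a period. SAP 14.1.2 item 6 reads "Proportion of patients admitted to intensive care at Day 7, 14 and 28 after randomization", and the schedule gives ICU as a yes/no item with no look-back. The window is undefined, on secondary endpoints.

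**Conclusion.** The concern holds as a mismatch between objective and endpoint. Need for oxygen or ventilation before day 14 is never scored as a failure on its own account in the primary clinical analysis, and no other inferential analysis takes first need as its event. That conclusion rests on the text alone.

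Its size rests on the assumed r, taken as equal across arms and with day-14 status standing for continuing need. For r from 0.1 to 0.5, power at 100 per arm would be 81% to 41% if recovered patients count as successes, and 86% to 65% if they are left out, against 88% with no loss. At 68 patients little power remains to lose, so the reason to act is that the primary result would not answer the primary objective.

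**What to change.** - In SAP 14.1.1, and in the matching day-7 and day-28 item of 14.1.2, score *Required* if supplemental oxygen or mechanical ventilation was needed, or the NEWS above 2 criterion was met, at any time from randomization through the stated day.
- Use the T7, T14 and T28 fields, eCRF endpoint records, concomitant-treatment records and discontinuation reasons. SAE forms alone will not do, because protocol 8.4.3 exempts trial endpoints from SAE reporting.
- Score withdrawal for meeting the oxygen or ventilation criteria as failure.
- Keep the day-14 status as a supportive analysis.
- Define the time-to-event analysis as time to first need.
- Reconcile protocol 6.2.4 and 6.3 on whether these patients remain in follow-up.
- List the changes in SAP section 18 before unblinding.

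As a separate, lesser point, state whether hospitalisation and ICU admission on days 7, 14 and 28 are cumulative. SAP 15.1.2 already does so for adverse events: "within Day 7, 14 and 28 after randomization will be analysed using comparison of proportions".

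The cost is SAP wording and one derived variable. The small downside is that need between visits depends on dated eCRF records.
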